12.2. Sample size Calculations

The sample size was determined using a one sample paired test assuming a one-sided type I error rate of 0.05 and a power greater than 90%. The TIR at baseline is assumed to be 60% and the TIR at 6 months follow up (TIR calculated using overall 6 months CGM data) is assumed to be 63% with same standard deviation as 16% and a correlation as 0.5. Thus, the hypothesis to be tested is:

$$H_0: \mu\text{TIR6m} - \mu\text{TIR baseline} = d_0$$

$$H_A: \mu\text{TIR6m} - \mu\text{TIR baseline} > d_0$$

where $d_0 = 3$ is the expected increase of TIR at 6 months. The sample size needed to demonstrate this hypothesis is 245 paired assessments per subject. The calculation is adjusted for loss-to-follow-up and protocol failures, including potential subjects with less than 70% of the time in Auto Mode with an assumption considering an attrition rate of 20%. The total number of subjects to be enrolled is 306.

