12.1. Sample size justification

The primary endpoint is to evaluate if the MiniMed™ 780G therapy in Auto Mode increases the proportion of Time In Range (TIR) at 6 months compared to the MiniMed™ 780G therapy in manual mode at baseline. The endpoint is the Time In Range (TIR) defined as the proportion of sensor glucose concentration within the target range 70-180 mg/dL (3.9-10.0 mmol/L).

The Pivotal study [12, 13] enrolled adolescents (ages 14–21 years) and adults (ages 22–75 years) with type 1 diabetes in a multicenter pivotal trial. The Medtronic MiniMed™ 670G system was used during a 2- week run-in phase without HCL control, or Auto Mode, enabled (Manual Mode) and, thereafter, with Auto Mode enabled during a 3-month study phase. The study has shown a significant

improvement on TIR of 60.4% (10.9%) to 67.2% (8.2%) in adolescents and from 68.8% (11.9%) to 73.8% (8.4%) in adults. Using this information and considering that this study is expected to include around 32 sites and including also patients aged >7 years old, a lower increase of TIR and higher variability are expected. The following assumptions were made:

- Improvement in TIR of at least 3% points at 6 months compared to the baseline.
- Standard deviation as 16% due to the mixed population and multiple sites expected for this study.

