14.7.4. Sponsor reporting requirements

Medtronic shall prepare and submit the following complete, accurate, and timely reports listed in the Table 5. In addition to the reports listed below, Medtronic shall, upon request of Competent Authorities provide accurate, complete and current information about any aspect of the study.

Table 5: Sponsor reporting requirements

Report	Submit to	Description
Premature termination or suspension of the study	Investigators, reviewing EC	Medtronic will provide prompt notification of termination or suspension and reason(s) to investigators. Medtronic will inform the reviewing EC.
Incident/Risk of Incident Withdrawal of device from market	Competent Authority	Medtronic will immediately inform Competent Authority if not already done by investigators.
Subject enrollment complete	Investigators	Medtronic will notify the investigators as soon as possible of the completion of the enrollment.
Statistical analysis plan	HAS	Medtronic will submit the statistical analysis plan, including analysis scheduled for each endpoint, before the analyses are performed.
Interim Report	HAS	Medtronic will submit the interim report of the study to HAS 6 months before the renewal deadline.
Final report	Investigators, and the HAS	Medtronic will provide investigators and the HAS with a copy of the final report of the study. Final study report must be available for ANSM in case of request

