4.1. Primary Objective and Endpoint

The primary objective is to evaluate if the treatment of T1D with MiniMed™ 780G System in pediatric and adult population increases the Time In Range (TIR) at 6 months compared to MiniMed™ 780G System in Manual Mode (with no SmartGuard™ functions) during the run-in period (expected to be approximately 2 weeks). TIR is defined as time spent of sensor glucose values within 70-180mg/dL (3.9–10.0 mmol/L).

The primary endpoint is the change in (%) the time spent within range (TIR) defined as the proportion of sensor glucose concentration within the target range 70-180 mg/dL (3.9–10.0 mmol/L) between baseline and 6 months.

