An overview of data collection is given in the Table 1.

Table 1: Schedule of assessments

Data collection	Enrollment /Baseline	6-month Follow-up (±45 days)	12-month Follow-up (±45 days)
Data Release Form	✓		
Inclusion and exclusion criteria	✓		
Demographics	✓		
Medical history	✓		
HbA1c¹	✓	✓	✓
Auto Mode Activation Date	✓		
Ensure that CareLink™ Personal upload was done²	✓ ⁴	✓	✓
CGM data	✓	✓	✓
Study Exit			✓
Study Deviation	Upon occurrence		
QUESTIONNAIRES :			
DTSQs	✓	✓	✓
DTSQc		✓	
DQoL³	✓	✓	✓
HFS	✓	✓	✓

1. Available HbA1c value collected up to 30 days before enrollment and more or less 30 days from 6-month and 12-month follow up visits can be used.
2. CareLink™ data should be uploaded via Bluetooth connectivity from the devices or via USB connection as per clinical practice, i.e. once a week. CareLink™ Data evaluation will be done every 3 months for secondary objectives.
3. DQoL will not be administered in case patient is between 7 and 12 years old.
4. Baseline CGM data will be collected before Auto Mode activation at the end of the run-in phase

6. Determination of Sample Size

The sample size was determined using a one sample paired test assuming a one-sided type I error rate of 0.05 and a power of 90%. The TIR at baseline is assumed to be 60% and the TIR at 6 months follow up (TIR calculated using overall 6 months CGM data) is assumed to be 63% with same standard deviation as 14% and a correlation as 0.5. Thus, the hypothesis to be tested is:

$$H_0: \mu_{TIR6m} - \mu_{TIR \text{ baseline}} = d_0$$

$$H_A: \mu_{TIR6m} - \mu_{TIR \text{ baseline}} > d_0$$

where $d_0 = 3$ is the expected increase of TIR at 6 months. The sample size needed to demonstrate this hypothesis is 245 paired assessments per subject. The calculation is adjusted for loss-to-follow-up and protocol failures, including potential subjects with less than 70% of the time in Auto Mode and with an assumption considering an attrition rate of 20%. The total number of subjects to be enrolled is 306.

[figure not shown]
7. Statistical Methods

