7.2. General Methodology

Descriptive statistics will be used to summarize patient characteristics. For categorical variables, the description will consist at least of the sample size, numbers of missing data and valid data, the frequency and the percentage of each category. Denominators for calculation of percentages will be taken as the number of subjects with available (not missing or unknown) observations in the specified patients sets and groups unless otherwise stated. Percentages will be presented with no decimal (or one decimal, if appropriate) and rounded to the nearest integer. For continuous variables, the description will consist at least of the sample size (N), number of subjects with non-missing observation (n), mean, standard deviation, standard error, minimum, median and maximum. For $n < 3$, only mean, minimum and maximum will be displayed. In general, minimums and maximums will be presented to the same level of accuracy as the raw data; means and medians will be presented to 1 further decimal place; if appropriate, standard deviation and standard error will be presented to 2 further decimal places.

Device data metrics will be derived in a real-world data setting using all the device data collected during the patient study exposure.

It is anticipated that SAS 9.4 or later (SAS Institute Inc., Cary, NC, USA) will be used to perform all statistical analyses. Statistical tests will be based on a one-sided significance level of 0.05, and possible interaction effects will be evaluated at a significance level of 0.10. No adjustments for multiple comparisons will be performed. Additional exploratory analyses will be conducted as deemed appropriate and described as ad-hoc analysis in the study report.

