7.9.1. Primary Endpoint

The primary endpoint on efficacy defined as the change of TIR at 6 months, calculated starting from the Auto Mode activation (Study phase) to the 6-months, with baseline (Run-In phase) will be analyzed by means of paired (samples) t-test or Wilcoxon signed rank sum test according to the normal or non-normal distribution.

The TIR will be calculated as the proportion (%) of sensor glucose concentration measurements within the target range of 70-180 mg/dL (3.9-10.0 mmol/L) on the total sensor glucose measurements.

The mean change will be displayed together with their 95% confidence interval (95%CI).

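### The primary null hypothesis in Protocol 12.2 and SAP 6 is set at the 3-point gain the trial assumes; the Protocol's 245 pairs and 90% power belong to a test against 0

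*Protocol*

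**What the plan says.** Protocol section 12.2 and SAP section 6 (Determination of Sample Size) set out the same pair of hypotheses. H0 is that mean TIR at 6 months minus mean TIR at baseline equals d0, and HA is that the difference exceeds d0, "where $d_0 = 3$ is the expected increase of TIR at 6 months". Both sections assume 60% at baseline and 63% at 6 months, use a one-sided type I error of 0.05, and arrive at 245 pairs and 306 enrolled after 20% attrition. The Protocol gives power above 90% and the SAP gives 90%.

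The two sections differ on variability. The Protocol sizes "with same standard deviation as 16% and a correlation as 0.5", the SAP "with same standard deviation as 14% and a correlation as 0.5".

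Elsewhere, Protocol 12.1 lists the 3 points as a planning assumption: "Improvement in TIR of at least 3% points at 6 months compared to the baseline". The primary objective, in SAP 4.1 and likewise in Protocol 5.1, asks whether treatment "increases the Time In Range (TIR) at 6 months compared to MiniMed™ 780G System in Manual Mode". SAP 7.9.1 says the primary endpoint "will be analyzed by means of paired (samples) t-test or Wilcoxon signed rank sum test according to the normal or non-normal distribution", and Protocol 12.3 describes the same test. Neither names a null value or a shift of 3. SAP 7.2 adds: "Statistical tests will be based on a one-sided significance level of 0.05".

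**The concern.** A sample size calculation needs two different values: the change under the null and the change assumed to be true. Here both are 3 points. As printed, the null is true under the trial's own planning assumptions, so the stated power cannot belong to the stated test.

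What is at stake is the success criterion for the primary endpoint. The hypothesis pair is the only formal statement of what the primary test must show. Read literally, the trial must show a gain above 3 points. Read through the objective and the unshifted paired test, it must show a gain above 0. An observed gain of exactly the 3 points planned for would fail on the first reading and succeed on the second, at the planned SD. A rejection could also be reported as evidence of more than 3 points when the test run was against 0. Under Protocol 14.7.4 the sponsor "will submit the statistical analysis plan, including analysis scheduled for each endpoint, before the analyses are performed" to HAS, so an outside body will read this text as the pre-specified criterion.

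**Working it through.** **Inputs.** From Protocol 12.2: baseline 60%, 6 months 63%, SD 16 at each time, correlation 0.5, one-sided alpha 0.05, 245 pairs, 20% attrition. From SAP 6: the same, except SD 14.

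**SD of the paired difference.** sqrt(2 × SD² × (1 − r)):
- Protocol: sqrt(2 × 16² × 0.5) = 16
- SAP: sqrt(2 × 14² × 0.5) = 14

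**Reproducing the plan's figure (null 0, true gain 3, SD 16).**
- Normal approximation: ((1.645 + 1.282) × 16 / 3)² = 243.6, so 244.
- Exact one-sided paired t-test (noncentral t): 244 pairs give power 0.8990 and 245 give 0.9000, so 245 is the smallest number reaching 90%.
- Attrition: 245 / 0.8 = 306.25, matching the stated 306.
- A two-sided 0.05 test would need 301 pairs and does not match.

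The Protocol's figures therefore come from a one-sided test against 0.

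**The hypothesis as printed (null 3).** The effective difference is the true gain minus 3. At the assumed gain it is 63 − 60 − 3 = 0, so power equals alpha, 5%, whatever the sample size. With 245 pairs:

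| True gain (points) | Power against 3, SD 16 | Power against 3, SD 14 | Pairs for 90% against 3, SD 16 | Pairs for 90% against 3, SD 14 |
|---|---|---|---|---|
| 3 | 5% | 5% | none suffices | none suffices |
| 4 | 25% | 30% | 2194 | 1680 |
| 5 | 62% | 72% | 550 | 421 |
| 6 | 90% | 96% | 245 | 188 |

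**Observed mean gain needed to reject (t-test, 245 pairs).** Null + t(0.95, 244) × SD of difference / sqrt(245), with t(0.95, 244) = 1.651:
- SD 16: 1.651 × 16 / 15.65 = 1.69. The threshold is 1.69 against 0 and 4.69 against 3.
- SD 14: 1.651 × 14 / 15.65 = 1.48. The threshold is 1.48 against 0 and 4.48 against 3.

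**SAP 6 on its own inputs (null 0, gain 3, SD 14).** The normal approximation gives ((1.645 + 1.282) × 14 / 3)² = 186.5. The exact t-test needs 188 pairs for 90%, and 245 pairs give 95.5%. Correcting the null alone therefore leaves SAP 6 inconsistent.

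**The case against.** The strongest reply is that this is a slip of notation in a sizing section. The objective says increases, the paired test carries no shift, the Protocol synopsis describes the sizing without d0, and 245 reproduces against 0. A statistician following SAP 7.9.1 would run the ordinary test against 0, and nothing in the data or programming would change. All of that stands, and it is why the conclusion is a wrong null and not an undersized trial. It does not remove the defect: neither SAP 7.9.1 nor Protocol 12.3 states a null value, so nothing in either document overrides the printed hypothesis.

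A second reply is that 3 might be a deliberate margin, since Protocol 12.1 speaks of at least 3 points and cites gains with the earlier 670G system of 67.2 − 60.4 = 6.8 points in adolescents and 73.8 − 68.8 = 5.0 in adults. Against a null of 3 with SD 16 and 245 pairs, those gains would give about 98% and 62% power. But the Protocol expressly expects a smaller gain than in that study, sizes on 63%, calls 3 the expected increase and never a margin, and assumes no larger gain under HA.

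Two limits also stand. The thresholds above apply to the t-test when the observed SD of change equals the planned value; the Wilcoxon option has no equivalent mean threshold. The SD discrepancy is a separate fault that would remain if the null were right. It is included because the same paragraph of SAP 6 has to be corrected.

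**Conclusion.** The concern holds. Both documents state a primary null under which the planned effect has a 5% chance of rejection, beside a claim of 90% power. The Protocol's 245 pairs and 90.0% power are correct for a one-sided paired t-test of 0 at a true gain of 3, SD 16 and correlation 0.5. Under those inputs the sample size stands.

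The practical size of the ambiguity is 3 points of observed TIR gain: results between about 1.7 and 4.7 points (SD 16), or 1.5 and 4.5 points (SD 14), change from success to failure depending on which null is used. That a null of 0 was intended is an inference from the objective, the unshifted test and the reproduced sample size; neither document says so. In SAP 6 there is a further mismatch, because 245 pairs at 90% power does not follow from SD 14 even against 0. The correction is needed before the primary analysis is run.

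**What to change.** 1. In Protocol 12.2 and SAP 6, write H0: mean change ≤ 0 against HA: mean change > 0, and describe 3 points as the difference assumed under HA for sizing.
2. In SAP 7.9.1, and in the matching text of Protocol 12.3, state that the paired test is against 0. The one-sided 0.05 level is already given in SAP 7.2 and Protocol 12.3.
3. In SAP 6, reconcile SD 14 with the Protocol's 16 so that SD, power and 245 agree. Restoring 16 reproduces 245 at 90.0%. If 14 is kept, give the reason and state 95.5% power at 245.
4. If 3 points was meant as a margin to exceed, say so, state the larger gain assumed under HA, and restate power and sample size. With SD 16, 90% power needs 550 pairs at a true gain of 5, or 245 at a gain of 6.

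Steps 1 to 3 are wording changes in four places plus one SD value, with no effect on enrolment, data or programming. Step 4 would require the sizing to be redone. The corrected SAP should be the one sent to HAS.

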12.3. Data Analysis

A detailed description of the statistical methods will be contained in the Statistical Analysis Plan (SAP). Any change to the data analysis methods described in this section and/or the SAP will require an amendment only if it changes a principal feature of the study description. Any other changes to the data analysis methods will be described and justified in the Final Report or publications.

Descriptive statistics will be used to summarize patient characteristics. For categorical variables, the description will consist at least of the sample size, numbers of missing data and valid data, the frequency and the percentage of each category. Denominators for calculation of percentages will be taken as the number of subjects with available (not missing or unknown) observations in the specified patients sets and groups unless otherwise stated. Percentages will be presented with no decimal. For continuous variables, the description will consist at least of the sample size (N), number of subjects with non-missing observation (n), mean, standard deviation, standard error, minimum,

median and maximum. For $n < 3$, only mean, minimum and maximum will be displayed. In general, minimums and maximums will be presented to the same level of accuracy as the raw data; means and medians will be presented to 1 further decimal place; if appropriate, standard deviation and standard error will be presented to 2 further decimal places.

Since the impact of missing data is expected to be small no multiple imputation method for missing data is planned. However, should the issue of missing data arise, the choice of the imputation method for missing data will depend on the pattern of missing data and the type of the imputed variable.

The study is a multicenter trial and a multicenter impact on primary outcomes will be investigated. A description by means summary statistics on primary outcomes by sites will be provided.

Outliers and influential observations will be identified via graphical plots. Once outliers or influential observations are identified, the study team will be informed and according to their decision the analysis for primary endpoint may be repeated excluding the outliers. Additional exploratory analyses will be conducted as deemed appropriate.

The primary analysis will be performed on the Intention To Treat (ITT) set and a sensitivity analysis will be performed using the Per Protocol set including all subjects that were compliant with the protocol.

The ITT includes all patients enrolled in the study those sign Data Release Form, fulfill the inclusion and exclusion criteria. The ITT will be used for all endpoints and safety evaluation. For patients who dropout the analyses will include all data up to the point of their last data collection.

The PP includes all patients enrolled in the study those sign Data Release Form, fulfill the inclusion and exclusion criteria and having at least 70% of time using the Auto Mode. The PP set will be used for all endpoints.

The primary endpoint on efficacy defined as the change of TIR at 6 months from Auto Mode activation at baseline will be analyzed by means of paired (samples) t-test or Wilcoxon signed rank sum test according to the normal or non-normal distribution. The mean change will be displayed together with their 95% confidence interval (95%CI). Additional exploratory analysis on the TIR change over time (baseline, 3, 6 and 12 months follow-up) will be analyzed by means of mixed models for repeated measures. The dependent variable will be pre-log transformed depending on normal or non-normal distribution. The model will have the clinical outcomes as dependent variables and baseline values and visits as explanatory variables. All assumptions for regression models will be performed by assessment of plots of the residual values. Difference between visits means will be tested by applying contrast on the estimated model. The plot for the mean change over time will be

reported.

The secondary endpoint on satisfaction defined by the DTSQc will be analyzed by means of one sample Z- score test. The DTSQc has six items related to treatment satisfaction and two other items assess perceived frequency of hyperglycemia and hypoglycemia. Each item has a maximum of 3 (more satisfied now) and a minimum of -3 (less satisfied now) with a midpoint of 0 reflecting no change. The scale total is computed by adding 6 items (1,4,5,6,7,8) and the 2 items on hypo/hyperglycemia will be analyzed separately. Previous studies on patients treated with MiniMed™ 640G pump have shown a good satisfaction using the DTSQc questionnaire. The sample size estimated would also allow us to demonstrate a positive DTSQc satisfaction score.

Other secondary endpoints on quality of life defined as the change from baseline will be analyzed by means of paired (samples) t-test or Wilcoxon signed rank sum test according to the normal or non-normal distribution. The mean change will be displayed together with their 95% confidence interval (95%CI).

The secondary endpoint on HbA1c change over time (baseline, 6- and 12-months follow-up) will be analyzed by means of mixed models for repeated measures. The dependent variable will be pre-log transformed depending on normal or non-normal distribution. The model will have the clinical outcomes as dependent variables and baseline values and visits as explanatory variables. All assumptions for regression models will be performed by assessment of plots of the residual values. Difference between visits means will be tested by applying contrast on the estimated model. The plot for the mean change over time will be reported.

It is anticipated that SAS (SAS Institute Inc., Cary, NC, USA) will be used to perform all statistical analyses. Statistical tests will be based on a one-sided significance level of 0.05, and possible interaction effects will be evaluated at a significance level of 0.10. No adjustments for multiple comparisons will be performed. Additional exploratory analyses will be conducted as deemed appropriate.

Procedures for reporting any deviation(s) from the original statistical plan including that justification will be documented.

13. Ethics

13.1. Statement(s) of Compliance

The study is designed to reflect the Good Clinical Practice (GCP) principles such as the protection of the rights, safety and well-being of human subjects, controls to ensure the scientific conduct and credibility of the clinical investigation and the definition of responsibilities of Medtronic and investigators.

Medtronic Controlled Information

The study will be conducted according to national and local laws, regulations, standards and requirements of the country in which the clinical study is conducted, including data protection laws, and according to the Clinical Investigation Agreement and the Clinical Investigation Plan.

The study will also be conducted in compliance with the latest version of the Declaration of Helsinki. The principles of the Declaration of Helsinki are implemented in this study by means of the patient Data Release Form (DRF) process, Ethics Committee approval, study training, clinical trial registration and publication policy.

Where applicable, regulatory authority notification will be done. Investigational sites will not be activated, nor begin enrolling subjects, until the required approval/favorable opinion from the respective Ethics Committee has been obtained (as appropriate).

Additionally, any requirements imposed by the regulatory agency or Ethics Committee shall be followed, as appropriate. Medtronic will be informed by the Ethics Committee and/or the investigator in case any action is taken by an Ethics Committee with respect to this investigation.

14. Study Administration

